
4.3 Withdrawal of Subjects

In accordance with the declaration of Helsinki and the applicable country's acceptance, each subject is free to withdraw from the study at any time, for any reason (e.g. lost to follow-up, withdrawal of consent, AE).

The investigator can withdraw a subject from the study at any time for any reason (e.g. protocol deviation, noncompliance with the protocol conditions, lack of cooperation, in the event of concurrent illness, AE, or other reasons concerning the health or well-being of the subject).

The reason for and date of withdrawal from the study must be recorded in the CRF.

If withdrawal is based on subject's decision every attempt will be made to determine:

- The reason for withdrawal,
- Whether the subject also decides to withdraw his consent for the sponsor to collect and use the data collected up to the withdrawal point.

Data collected prior to subject withdrawal may be kept in study records and shared with for further analyses unless the subject formally specifies his decision to withdraw consent for using data already collected.

If the reason for withdrawal is an AE or a clinically significant laboratory test abnormality, monitoring will continue until the event has resolved or stabilised, until the subject is referred to the care of a local health care professional, or until a determination of a cause unrelated to the study drug or study procedure is made. The specific AE(s) or test result(s) must be recorded in the CRF.

Should a subject drop out or be withdrawn from the study after study drug administration and before normal study completion, all efforts will be made to complete the follow-up end-of-study assessments and report the observations up to the time of withdrawal as thoroughly as possible. A complete final evaluation at the time of the subject's withdrawal should be made whenever possible.

Any subject who drops out or is discontinued from the study before normal study completion may be replaced at the discretion of the sponsor. Replacement subjects will receive the same schedule and treatment as the subject they replace.

All cases of discontinuation will be discussed between the investigator and the sponsor.

5 STUDY CONDUCT

5.1 Study Schedule of Assessments

The schedule of procedures and assessments during the study is summarised and presented in Section 18.1.

The total volume of blood drawn for each subject and all evaluations throughout this study is detailed and presented in [Section 18.2](#).

5.2 Study Visits and Procedures

5.2.1 *Informed Consent*

After a subject has received explanations and responses to his potential questions about the study by the investigator (or designee) and has been given reasonable time to think about it, a signed and dated informed consent form will be obtained prior to any study procedures.

5.2.2 *Screening*

After informed consent is obtained, screened subjects will be allocated a study-specific subject number which must comply with formatting specifications provided by the sponsor.

All screened subjects must be identifiable throughout the study. The investigator will maintain a list of all subjects screened with subject numbers and names to enable records to be found at a later date if required. Records up to the time of premature termination or normal study completion should be completed. In the event that a subject is screen failure or does not receive study treatment, the primary reason will be recorded.

The subjects with severely impaired renal function and the healthy subjects will attend the clinical unit for an outpatient visit to enter the screening period within 28 days prior to dosing on Day 1.

Once four subjects with severely impaired renal function and the four matching healthy subjects will be dosed, screening of reserve subjects with mildly and moderately impaired renal function may be initiated. The screening period will be extended to 56 days for these two groups. Screened subjects with mildly and moderately impaired renal function will however not be dosed before decision by the DRC and completion of the eight subjects with severely impaired renal function and the eight healthy subjects with normal renal function.

During the screening visit, screening tests and assessments will be performed to check compliance with inclusion/exclusion criteria and study requirements in order to confirm subjects' eligibility prior to enrolment.

The screening procedures detailed in [Section 18.1](#) will be performed during outpatient visits.

Detailed clinical laboratory tests are listed in [Section 18.3](#).

Subjects will not be allowed to be screened more than once, except reserve subjects who might be re-screened only once.

5.2.3 *Admission at the Clinical Unit*

Subjects will be admitted at the clinical unit on Day-1 of the study (start of the confinement period at the clinical unit).

Upon admission, compliance with inclusion/exclusion criteria will be confirmed, before assessment and collection of baseline parameters as listed in [Section 18.1](#) and detailed in [Section 18.3](#) for clinical laboratory parameters.

5.2.4 Dosing and Follow-up after Dosing

Subjects will be dosed on Day 1 in the morning.

They will then be followed postdose for safety assessments and sampled for PK evaluation (blood and urine), as presented in the study schedule of assessments [Section 18.1](#). A detailed list of clinical laboratory test is also presented in [Section 18.3](#).

In accordance with the investigator decision, subjects will have the option either to stay at the clinical unit up to Day 4 postdose or be discharged on Day 2 postdose. In this latter case, subjects will be requested to come back to the clinical unit for outpatient visits on Day 3 and Day 4 for blood sampling and supply of urines collected at home.

Subjects staying at the clinical unit up to Day 4, will be examined on Day 2 as listed in the study schedule of assessments [Section 18.1](#). The list of expected clinical laboratory tests is detailed in [Section 18.3](#).

5.2.5 Discharge

Discharge may happen on Day 2 or Day 4. The safety procedures to be conducted before discharge are detailed in the study schedule of assessment [Section 18.1](#). The list of expected clinical laboratory tests is detailed in [Section 18.3](#).

5.2.6 Early Discontinuation or End of Study Visit

Subjects will be discontinued from the study after completion of an EOS visit for follow-up safety assessments, which will happen between Day 8 to Day 15 after dosing, or earlier in case of early discontinuation.

Subjects who participate in the study in compliance with the protocol for at least eight days following study drug administration will be considered to have completed the study.

For subjects who complete the study, or for those who withdraw prematurely from the study, final safety procedures are listed in [Section 18.1](#). Detailed clinical laboratory tests are also provided [Section 18.3](#).

5.3 Lifestyle Restrictions

Besides restrictions already presented in the exclusion criteria, subjects will be requested to avoid the following from 48 hours prior to Day -1 and until discharge from the study or early discontinuation:

- Strenuous physical activity,
- Poppy-seeds consumption.

5.4 Priority Order on Study Procedures

When several assessments have to be performed at the same timepoint, they must be done in the following order:

- Blood samples for PK assessments,
- Blood samples for protein binding,
- Vital signs,
- 12 lead-ECG,
- Clinical laboratory samples.

6 TREATMENT OF SUBJECTS

6.1 Study Drug

Study drug administration will occur under medical supervision.

A single dose of 250 mg telotristat ethyl will be given under fed conditions (i.e. between 15 minutes before and 1 hour after the meal or snack).

6.2 Concomitant Medications

Unless otherwise specified (i.e. in the inclusion/exclusion criteria), concomitant medications are to be avoided during the study unless required to treat an AE or an ongoing medical problem.

Subjects with renal impaired function must be stable (dosage, regimen) as defined in the inclusion criteria. Any change in concomitant medication use, whether drug, dose, frequency or route, will be documented.

Any morning dose of H₂ receptor antagonists, proton pump inhibitors, or any known carboxyesterase inhibitor intake will be postponed to 4 hours postdose.

Any prior or concomitant medication given to a subject 30 days prior to dosing and during the study will be indicated in the CRF. Dose and trade name will be indicated.

6.3 Subject Compliance Monitoring

The investigator will be responsible for monitoring subject compliance.

Monitoring procedures will be described in a stand-alone document.

The investigator is responsible for the validity of all data collected at the site.

The sponsor is responsible for monitoring these data to verify that the rights and well-being of subjects are protected, study data are accurate (complete and verifiable to source data), and that the study is conducted in compliance with the protocol, GCP, and regulatory requirements.

Sponsor assigned study monitor will conduct regular site visits. The investigator will allow direct access to all relevant files (for all subjects) and clinical study supplies (dispensing and storage areas) for the purpose of verifying entries made in the CRF, and assist with the monitor's activities, if requested.

Adequate time and space for monitoring visits should be made available by the investigator.

The CRF is expected to be completed an ongoing basis to allow regular review by the study monitor, both remotely by the internet and during site visits. The study monitor will use functions of the electronic data capture (EDC) system to address any queries raised while reviewing the data entered by the study site personnel in a timely manner.

Whenever a subject name is revealed on a document required by the sponsor (e.g. laboratory print outs) the name must be blacked out permanently by the site personnel, leaving the date of birth visible, and annotated with the subject number as identification.

7 SAFETY ASSESSMENTS

The following safety parameters will be collected and reviewed during the study at specific timepoints as described in the study schedule of assessments in [Section 18.1](#).

- Adverse events,
- Concomitant medications,
- Medical and surgical history,
- Physical examination (including height, body weight, body temperature),
- Vital signs (including pulse, and diastolic and systolic blood pressures),
- 12-lead ECG,
- Clinical laboratory tests including haematology, blood biochemistry, coagulation and urinalysis.

Further routine medical assessments or any additional safety procedures may be performed during the study, if warranted and agreed upon between the sponsor and the investigator, or when clinically indicated.

The investigator will be responsible for a clinical assessment of the study participants during the whole participation of the subjects in the study, from informed consent up to discharge from the study, and for setting up of a discharge plan if needed.

Every effort should be made to ensure that all safety evaluations are completed by the same individual who made the initial baseline determination.

The sponsor global patient safety physician will monitor safety data throughout the course of the study.

Any clinically significant finding that result in a diagnosis should be recorded as an AE from the time informed consent is given.

7.1 Adverse Events

Adverse events will be monitored from the time that a subject gives informed consent and throughout the study, and will be elicited by direct, nonleading questioning or by spontaneous reports.

7.1.1 *Definition of an Adverse Event*

An AE is the development of an undesirable medical condition or the deterioration of a pre-existing medical condition, whether or not considered causally related to the study drug. An undesirable medical condition can be symptoms (e.g. nausea, chest pain), signs (e.g. tachycardia, enlarged liver) or the abnormal results of an investigation (e.g. laboratory findings, ECG).

An AE can include an undesirable medical condition occurring at any time, even if no study drug has been administered.

This definition includes events occurring from the time of the subject giving informed consent until the EOS/Early Discontinuation (ED).

7.1.2 *Adverse Events Categorisation, Recording, and Follow-up*

For all AEs, sufficient information should be obtained by the investigator to determine the causality of the AE (i.e. study drug administration, study procedure or other illness). The investigator is required to assess causality and record that assessment in the CRF.

Adverse events will be classified by the investigator as mild, moderate or severe according to the following criteria:

- **Mild:** Symptoms do not alter the subject's normal functioning,
- **Moderate:** Symptoms produce some degree of impairment to function, but are not hazardous, uncomfortable or embarrassing to the subject,
- **Severe:** Symptoms definitely hazardous to well-being, significant impairment of function or incapacitation.

The relationship of an AE to IMP administration will be classified by the investigator according to the following:

- **Related:** Reports including good reasons and sufficient information (e.g. plausible time sequence, dose-response relationship, pharmacology) to assume a causal relationship with study drug administration in the sense that it is plausible, conceivable or likely,
- **Not related:** Reports including good reasons and sufficient information (e.g. implausible time sequence and/or attributable to concurrent disease or other drugs) to rule out a causal relationship with IMP administration.

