1.8 Known and Potential Risks to Human Subjects

The most commonly reported adverse reactions in subjects with carcinoid syndrome treated with telotristat etiprate were abdominal pain, gamma-glutamyl transferase increased and fatigue. They were generally of mild and moderate intensity. In the clinical program supporting EU and United States (U.S.) approvals, the most frequently reported adverse reaction leading to discontinuation of treatment was abdominal pain in 7.1% subjects.

As part of the clinical development programme, safety of telotristat etiprate was also assessed in male and female healthy subjects. In a single ascending dose study (18), telotristat etiprate

was well tolerated in healthy subjects at single doses up to 500 mg, with gastrointestinal (GI)-related adverse events (AEs) (diarrhoea, nausea, abdominal distension, constipation) reported at the 1000 mg and 1500 mg dose. There were no clinically significant laboratory or electrocardiogram (ECG) abnormalities.

This study is considered to present a limited and acceptable risk profile to the protocol specified populations.

As renal excretion is a minor elimination pathway for telotristat etiprate (less than 1% of the administered dose recovered from the urine), a staged clinical trial design is proposed for assessing the effects of impaired renal function on the PK of telotristat ethyl and its active metabolite (telotristat) (a potential design mentioned in the European Medicines Agency (EMA) (22) and Food and Drug Administration (FDA) (23) guidelines for non-renally eliminated drugs).

2 STUDY OBJECTIVES**2.1 Primary Objective**

To compare the pharmacokinetics (PK) of telotristat ethyl and its active metabolite (telotristat) following a single oral dose of 250 mg telotristat ethyl in subjects with renal impaired function versus healthy subjects with normal renal function.

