3.2.3.1 Adverse events

AEs will be coded using the Medical Dictionary for Regulatory Activities (MedDRA) with the current version at Ipsen coding department at the time of database lock.

Listings will be presented and sorted by renal impaired function group, subject, start date-time, primary system organ class, preferred term and reported term for all AEs recorded during the study.

Listings of all AEs, serious adverse events (SAE), AEs leading to withdrawal and listing of deaths will also be presented.

Treatment Emergent Adverse Events (TEAE) will be flagged (*) in the listing of AEs and will be summarised.

A TEAE is defined as any AE that occurs during the active phase of the study (from the time of the subject giving informed consent until the EOS/early withdrawal) if:

- it was not present prior to administration of IMP, or
- it was present prior to administration of IMP but the intensity increased after administration of IMP.

An overall summary table of all AEs will be presented.

TEAEs will be summarised by renal function group with the number and percentage of subjects with AEs classified by primary system organ class and preferred term. The number of occurrences of a TEAE will also be presented.

In addition, summary tables will also be presented for SAEs, serious TEAEs, TEAEs by decreasing frequency, TEAEs by maximum intensity, TEAEs by most serious causality and TEAEs leading to premature study withdrawal.

In case of missing intensity, the intensity will be considered as severe and in case of missing causality, the causality will be considered as related.

In the event of multiple reports of the same preferred term being reported by the same subject, the maximum intensity (severe > missing > moderate > mild) and the most serious causality (related > not related) will be chosen.

3.2.3.2 *Laboratory data*

3.2.3.2.1 *Standardisation*

As in this study several laboratories are involved in the assessment of biological samples, a standardisation method will be used in order to take into account the differences between the reference ranges of these laboratories.

The laboratory which analyses the majority of the samples will be used as the reference laboratory.

In a general way, standardised values will be assessed using the following formula:

$$X_{St} = X_{LRef} + (X_{URef} - X_{LRef}) \frac{X - X_L}{X_U - X_L} \text{ where}$$

X = measured value

X_L = lower limit value for the laboratory of the measured value

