14.3 SAFETY DATA

14.3.1 Displays of adverse events

Table	14.3.1.1:	Overall Summary of Adverse Events – Safety Population
-------	-----------	---

Table 14.3.1.2: Number (%) of Subjects Reporting Treatment Emergent Adverse Events by Primary System Organ Class and Preferred Term – Safety Population

Table 14.3.1.3: Number (%) of Subjects Reporting Serious Adverse Events by Primary System Organ Class and Preferred Term – Safety Population

Table 14.3.1.4: Number (%) of Subjects Reporting Serious Treatment Emergent Adverse Events by Primary System Organ Class and Preferred Term – Safety Population

Table 14.3.1.5: Number (%) of Subjects Reporting Treatment Emergent Adverse Events Leading to Withdrawal by Primary System Organ Class and Preferred Term – Safety Population

Table 14.3.1.6: Number (%) of Subjects Reporting Treatment Emergent Adverse Events by Decreasing Frequency of Preferred Term – Safety Population

Table 14.3.1.7: Number (%) of Subjects Reporting Treatment Emergent Adverse Events by Maximum Intensity – Safety Population

Table 14.3.1.8: Number (%) of Subjects Reporting Treatment Emergent Adverse Events by Most Serious Causality – Safety Population

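### The definition of a moderate adverse event rules out discomfort, so an uncomfortable, partly impairing, non-hazardous event fits none of the three grades

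*Protocol*

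**What the plan says.** Protocol 7.1.2 allows three grades and no other category: "Adverse events will be classified by the investigator as mild, moderate or severe according to the following criteria". The definitions are:

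- Mild: normal functioning is left unchanged.
- Moderate, the middle grade: "Symptoms produce some degree of impairment to function, but are not hazardous, uncomfortable or embarrassing to the subject".
- Severe: there is a definite hazard, or impairment is significant, or the subject is incapacitated.

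The SAP uses the grade in two ways. Its list of tables includes Table 14.3.1.7, "Number (%) of Subjects Reporting Treatment Emergent Adverse Events by Maximum Intensity", the only planned adverse event table broken down by intensity. SAP 3.2.3.1 also makes intensity part of the definition of a treatment-emergent event: one already present before dosing counts only if it became more intense afterwards. The same section sets a rule for blanks: "In case of missing intensity, the intensity will be considered as severe".

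No other section of either document redefines the grades. SAP section 5, on changes from the protocol, does not mention them.

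**The concern.** The three definitions should together cover every event, and they do not. Moderate is the grade one would expect for a symptom that is unpleasant and gets somewhat in the way, yet its wording excludes anything unpleasant. Nausea that makes a subject cut back on activity, without danger or serious limitation, is a natural example.

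An investigator with such an event has to depart from the text in some direction: down to mild, up to severe, or to moderate against its wording. The Synopsis plans four clinical units, and nothing in the documents tells them to choose alike. The comparison of safety and tolerability between renal function groups is a secondary objective with no formal testing, so readers will rely on the raw counts. Those counts could then partly reflect how each unit resolved the wording. The boundary between mild and moderate also matters for symptoms present before dosing, because a recorded step up in intensity is what brings such an event into the treatment-emergent tables.

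**Working it through.** The documents state no figure on this point, so the check is one of logic.

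**Inputs.** The three definitions come from Protocol 7.1.2. Each event is described by impairment of function (none, some, significant), hazard (no, yes) and discomfort or embarrassment (no, yes), which gives 3 × 2 × 2 = 12 profiles. Incapacitation is counted with significant impairment.

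**Rules applied.**

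- Mild: no impairment and no hazard. The protocol's mild definition does not mention hazard. A hazardous event without impairment is assigned to severe here, which does not affect the result.
- Severe: hazard, or significant impairment.
- Moderate, literal reading: some impairment, no hazard, no discomfort.
- Moderate, discomfort permitted: some impairment, no hazard.
- Moderate, discomfort required: some impairment, no hazard, discomfort present.

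| Impairment | Hazard | Discomfort | Profiles | Literal | Permitted | Required |
|---|---|---|---|---|---|---|
| None | No | No | 1 | Mild | Mild | Mild |
| None | No | Yes | 1 | Mild | Mild | Mild |
| None | Yes | Either | 2 | Severe | Severe | Severe |
| Some | No | No | 1 | Moderate | Moderate | **No grade** |
| Some | No | Yes | 1 | **No grade** | Moderate | Moderate |
| Some | Yes | Either | 2 | Severe | Severe | Severe |
| Significant | Either | Either | 4 | Severe | Severe | Severe |
| **Ungraded** | | | **of 12** | **1** | **0** | **1** |

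**Results.** The literal text leaves one profile without a grade: some impairment, no hazard, discomfort present. The gap is confined to that cell. An uncomfortable event with no impairment is mild, and one with significant impairment is severe.

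The last two columns matter for the repair. Requiring discomfort, as in not hazardous but uncomfortable or embarrassing, only moves the gap to the event that impairs function without discomfort. Permitting discomfort closes it.

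**What happens to a blank.** If a grade were missing and stayed missing, SAP 3.2.3.1 would count it as severe. That section also ranks repeated reports of one preferred term by "the maximum intensity (severe > missing > moderate > mild". Taking the pairs in turn:

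- severe with missing gives severe;
- missing with moderate gives missing, counted as severe;
- missing with mild gives missing, counted as severe.

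The reported grade is the same as if missing ranked level with severe.

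**The case against.** The strongest reply is that this is a drafting slip. Most investigators would grade such an event moderate by common sense, and the training that Protocol section 15 places before screening is an occasion to align them. That is fair and lowers the expected harm, but it means relying on sites to set aside the text, and nothing in the documents tells them to.

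A second reply is that few such events may occur. Protocol 1.8 names "abdominal pain, gamma-glutamyl transferase increased and fatigue" as the commonest reactions, but in treated carcinoid syndrome patients, and a laboratory increase is not in itself an uncomfortable symptom. In healthy subjects the same section reports good tolerability at single doses up to 500 mg, with gastrointestinal events at 1000 and 1500 mg, whereas this study gives a single 250 mg dose. This stands: the documents do not show how often the gap would be met.

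Third, the consequences are bounded. Seriousness does not depend on intensity, withdrawal rules do not use it, and SAP 3.2.3.1 lists every event by subject with its reported term. With 16 to 32 subjects, a reader can inspect each one. This also stands.

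A reader might infer three stronger points that the documents do not support:

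- **That ungradable events will be counted as severe.** Protocol 7.1.2 requires a grade, the Data Management section calls for queries on missing or inconsistent data, and 15.3.2 asks for reasons for missing data. The route exists only if a blank survives all of that. Counting a missing grade as severe is an ordinary conservative rule.
- **That the SAP ranking contradicts its own rule for blanks.** As worked through above, it changes no reported grade once missing is counted as severe.
- **That the Part B decision is exposed.** The interim analysis covers safety data, but Protocol 11.4.5 and SAP 3.2.17 base the decision on a 2-fold increase in telotristat peak concentration or exposure. Neither gives intensity a role.

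**Conclusion.** The definition of moderate is wrong as written and should be corrected. Its size is minor. One of 12 profiles has no grade, and the damage is inconsistent classification in a descriptive safety table, plus some uncertainty over which pre-existing events count as treatment-emergent. The primary pharmacokinetic comparison and the Part B criterion are untouched.

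No numerical effect on the intensity table can be given. With eight subjects per group, one regraded subject is 1/8 = 12.5 percentage points, but that holds for any misclassification in a group this small and says nothing about how often this one would occur.

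The conclusion assumes that the negative governs the whole list in the moderate definition, which is its plain reading, that hazard is judged as present or absent, and that no CRF guide or training document outside the protocol and SAP already corrects the wording.

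**What to change.** In Protocol 7.1.2, reword moderate along these lines: *function is impaired to some degree; symptoms may be uncomfortable or embarrassing, but they are not hazardous to the subject*. The words may be are needed, since making discomfort a requirement would open a different gap. Leave mild and severe as they are.

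Use the same sentence in the CRF completion guide so that all units grade alike. The SAP needs no change: neither its rule for missing intensity nor its ranking has to be altered.

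The cost is one sentence in the protocol and one in the guide. It adds no procedure, visit or data item.
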